### **1.8.5 Supportive analyses**

Not applicable.

### **1.8.6 Secondary variables**

### **1.8.7 Methods of analysis**

#### **Maintenance of response**

Maintenance of response is defined as follows:

- for subjects in the fixed interval regimens, maintenance of response is defined as PASI 75 response at Weeks 104 and 156
- for subjects in the start of relapse regimens maintenance of response is defined as

- PASI 75 response at Weeks 92 and 144 for subjects who do not require active treatment at Week 92 or 144 and
- PASI 75 response at Weeks 104 and 156 for subjects who do require active treatment at Week 92 or 144.

Summary statistics of Maintenance of response will be presented in contingency tables and will include absolute and relative frequencies. Confidence intervals for response rates will be derived as well based on the score method including continuity correction ([Newcombe 1998](#)).

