2.2 Secondary objectives

- To evaluate the long-term efficacy of 150 mg and 300 mg of secukinumab administered at the start of relapse versus fixed interval regimens of 150 mg and 300 mg of secukinumab respectively, in subjects with moderate to severe chronic plaque-type psoriasis who are PASI 75 responders at Week 12, with respect to PASI 75 response:
 - at Weeks 104 and 156, for subjects in the fixed interval regimens, or
 - at Weeks 92 and 144, for subjects in the retreatment at start of relapse regimen who do not require active treatment at Week 92 or 144, respectively, or
 - at Weeks 104 and 156, for subjects in the retreatment at start of relapse regimen who do require active treatment at Week 92 or 144, respectively.
- To evaluate the efficacy of secukinumab treatment regimens in subjects with moderate to severe chronic plaque-type psoriasis with respect to PASI 50/75/90/100 and IGA 0 or 1 response over time.
- To evaluate the effects of treatment regimens with secukinumab in subjects with moderate to severe chronic plaque type psoriasis with respect to PASI score and IGA mod 2011 score over time
- To assess the effects of secukinumab treatment regimens with respect to EQ-5D score over time
- To investigate the effects of treatment regimens with secukinumab in subjects with moderate to severe chronic plaque-type psoriasis with respect to changes in DLQI over time
- To investigate the effects of treatment regimens with secukinumab in subjects with moderate to severe chronic plaque-type psoriasis with respect to DLQI 0 or 1 achievement over time

- To investigate the potential development of immunogenicity against secukinumab
- To investigate the occurrence of relapses (achieved maximal PASI improvement from baseline in core study is reduced by >50%) and rebounds in subjects on secukinumab therapy

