## 1.2 Subjects and treatments

The following analysis sets will be used for the data analysis.

**Extension Full analysis set (FAS):** The FAS will be comprised of all subjects from the randomized set to whom study treatments has been assigned and entered the extension study. Following the intent-to-treat principle, subjects will be analyzed according to the treatment assigned to at randomization in A2304 and A2307 and thereafter reassigned to treatment at Week 156. If the actual stratum is different to the assigned stratum in IRT, the actual stratum will be used in analyses.

Of note, subjects excluded from the randomized set will be excluded from the FAS.

**Extension Safety set:** The safety set includes all subjects who took at least one dose of study treatment during the extension treatment period. Subjects will be analyzed according to treatment received. The treatment received will be set to the treatment randomized. But if a subject has received the wrong treatment during the entire study, the treatment received will be set to this wrong treatment.

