**Table 1-1 Subject classification rules**

| Analysis set            | PD Population Codes that cause subject to be excluded | Non-PD criteria that cause a subject to be excluded |
|-------------------------|---|---|
| FAS (Full Analysis Set) | GCP01, GCP06, INCL01, INCL16, INCL18                  | No post baseline efficacy assessment                |
| Safety                  | GCP01, GCP06, INCL01, INCL16, INCL18                  | Not treated in the extension                        |

Note: Protocol Deviation (PD) Populations Codes are available from the study DHP (Data Handling Plan).

**Core study A2304:** Randomization was stratified by geographical region and by body weight collected at Visit 2 (< 90 kg or  $\geq$ 90 kg). In study sites selected for psoriatic arthritis assessments according to ACR criteria, randomization was also stratified according to history of psoriatic arthritis at screening.

Subjects were randomized using a 1:1 ratio into one of the treatment groups below:

- **Secukinumab 150 mg group:** AIN457 150 mg s.c. q week x 5 followed by 150 mg s.c. q 4 weeks
- **Secukinumab 300 mg group:** AIN457 300 mg s.c. q week x 5 followed by 300 mg s.c. q 4 weeks

At Week 12 in core study A2304, subjects were classified into 3 categories:

**PASI non-responders:** were discontinued from study

**PASI partial responders:** were offered participation into trial CAIN457A2307.

**PASI 75 responders:** within each dose group (150 or 300 mg s.c.) were re-randomized to one of the two maintenance treatment arms in a ratio of 1:1 (either “fixed interval” or “retreatment at start of relapse”) from Week 12 to Week 48.

Thus re-randomization will result to four treatment arms overall in A2304 and also one treatment arm in A2307:

**Fixed-time interval regimen – “FI” either 150 or 300 mg s.c. secukinumab:** In the maintenance period subjects will receive the same dose they received during the induction period. Thus, secukinumab 150 mg subjects will continue to receive 150 mg secukinumab every four weeks, and secukinumab 300 mg subjects will continue to receive 300 mg secukinumab every four weeks, from week 12 up to and including week 48.

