### **1.8.3 Testing strategy**

No formal hypothesis testing will be performed for this extension study.

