### 2.2 Analysis of binary (and categorical) data

#### 2.2.1 Summary statistics for binary and categorical data

Summary statistics for discrete variables will be presented in contingency tables and will include absolute and relative frequencies. If applicable, confidence intervals will be derived as well based on the score method including continuity correction [Newcombe 1998]:

With  $z$  as (1-alpha/2)-quantile of the standard normal distribution (SAS:  $z=PROBIT(1-\alpha/2)$ ),  $n$  as total number of subjects (i.e. number of subjects in the denominator), and  $p$  as estimated crude incidence (number of subjects with event /  $n$ ) it is  $q=1-p$

Then the lower limit is for  $p > 0$ , ( $L = 0$  for  $p = 0$ ),

$$L = \max \left( 0, \frac{2np + z^2 - 1 - z\sqrt{z^2 + 2 - \frac{1}{n} + 4p(nq + 1)}}{2(n + z^2)} \right)$$

and the upper limit is for  $p < 1$ , ( $U = 1$  for  $p = 1$ ),

$$U = \min \left( 1, \frac{2np + z^2 + 1 + z\sqrt{z^2 + 2 - \frac{1}{n} + 4p(nq - 1)}}{2(n + z^2)} \right).$$

For time courses of response variables, the point estimate at each time point including 95% confidence interval will be plotted.

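### The leading secondary objective compares start-of-relapse with fixed-interval dosing, but the SAP plans no between-regimen difference or interval for the re-randomised arms

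*SAP*

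**What the plan says.** Protocol 2.2 and SAP 1.1 word the first secondary objective as a comparison within dose, in Week 12 PASI 75 responders: secukinumab "administered at the start of relapse versus fixed interval regimens of 150 mg and 300 mg of secukinumab respectively". SAP 1.8.1 calls maintenance of response the main secondary efficacy analysis.

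The arms come from the core study, where SAP 1.2 says Week 12 responders in each dose group were "re-randomized to one of the two maintenance treatment arms in a ratio of 1:1". Protocol 5.2 keeps those arms until Week 156, when the investigator may switch three of the four to 300 mg every four weeks.

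The planned analysis in SAP 1.8.7 is: "Summary statistics of Maintenance of response will be presented in contingency tables and will include absolute and relative frequencies". The next sentence adds: "Confidence intervals for response rates will be derived as well based on the score method including continuity correction". Protocol 9.5.1 plans the same. SAP Table 1-14 lists only categorical summaries for this variable, and SAP 1.8.2 (hypothesis, model, method) and 1.8.5 (supportive analyses) are marked not applicable. SAP 1.8.3 states: "No formal hypothesis testing will be performed for this extension study".

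SAP Table 1-2 marks maintenance of response only for groups split by the Week 156 switch. The combined 150 mg FI column exists but is not marked for this endpoint, and there is no combined SoR column at either dose. Only 300 mg FI, which had no switch option, appears whole.

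**The concern.** An objective worded as one regimen versus another calls for an estimate of the difference and its uncertainty. The plan gives a rate and an interval for each group and stops there. A reader is left to compare intervals by eye, and overlap of two single-arm intervals is not a sound guide to whether the difference is distinguishable from zero.

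The layout adds to this. The switch is an investigator decision at Week 156, after the Week 104 outcome and at the visit that supplies the later one. Rates split by that decision condition on a choice that may itself depend on response, so neither subgroup's rate is the rate of the randomised arm.

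At stake is the reading of the main secondary efficacy result, not the primary objective, which is safety.

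**Working it through.** **Inputs from the documents.** Protocol 9.7: 918 planned in the core study, 5% drop-out to Week 12, a further 15% after, 80% PASI 75 response at Week 12, 148 per group. SAP 1.2: 1:1 allocation to FI or SoR within dose. Confidence level 95%: SAP 2.2.1 states it for response time courses ("the point estimate at each time point including 95% confidence interval will be plotted"); it is assumed here for maintenance of response.

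**Inputs assumed.** The documents give no maintenance rate for either regimen. FI is taken at about 80%, and SoR is varied. A smaller size of 110 per arm is also assumed, because Protocol 3.1 reports 675 enrolled against about 740 expected.

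**The plan's own figures first.**
- 918 × 0.95 × 0.85 = 741.3 (stated: about 740).
- 918 × 0.95 × 0.80 × 0.85 / 4 = 148.3 (stated: about 148).
- 1 − 0.999^148 = 13.8% and 1 − 0.99^148 = 77.4% (stated: about 14% and 77%).

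All reproduce, but the last two concern detecting an adverse event. No figure is stated for SoR versus FI.

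**Arm intervals.** The SAP's continuity-corrected score interval was used, with the lower limit as printed in SAP 2.3.1. SAP 2.2.1 prints one sign differently (z² + 2 for z² − 2). That moves the lower limit for 118/148 from 72.2% to 72.0% and changes no overlap result below.

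**Difference interval.** Newcombe's hybrid score interval, with (l, u) the score limits of each arm without continuity correction and d = p1 − p2:
- lower = d − √[(p1 − l1)² + (u2 − p2)²]
- upper = d + √[(u1 − p1)² + (p2 − l2)²]

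**Worked example, 148 per arm, FI 118 and SoR 101 responders.**
- FI: 79.7%, SAP interval 72.2 to 85.7. SoR: 68.2%, SAP interval 60.0 to 75.5. These overlap.
- d = 0.7973 − 0.6824 = 0.1149. Score limits without correction: 0.7254 to 0.8542 and 0.6036 to 0.7520.
- Lower = 0.1149 − √(0.0719² + 0.0696²) = 0.015. Upper = 0.1149 + √(0.0569² + 0.0788²) = 0.212.
- FI minus SoR is 11.5 points (1.5 to 21.2), which excludes zero.

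**Range where the two readings disagree.** Lowering the SoR count one subject at a time:

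| Per arm | FI | SoR counts | Observed differences |
|---|---|---|---|
| 148 | 118 | 103 down to 96 | 10.1 to 14.9 points |
| 110 (assumed) | 88 | 75 down to 69 | 11.8 to 17.3 points |

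Inside these ranges the difference interval excludes zero and the arm intervals overlap. Just below, 118 against 104 gives 9.5 points (−0.4 to 19.1), which includes zero. At 118 against 89 (19.6 points, 9.2 to 29.4) the arm intervals separate and both readings agree.

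**Effect of the switch split (assumed figures).** Take a SoR arm of 148 with 60% response, where 40% of responders and 70% of non-responders switch. Non-switchers: 0.60 × 0.60 = 0.36 responders and 0.30 × 0.40 = 0.12 non-responders, so 0.36/0.48 = 75%. Switchers: 0.40 × 0.60 = 0.24 and 0.70 × 0.40 = 0.28, so 0.24/0.52 = 46%. The table would show 75% and 46%; the arm's rate is 60%.

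**The case against.** The strongest reply is that descriptive reporting is deliberate. The primary objective is safety, no testing is planned, Protocol 3.4 says no comparators are used, and Protocol 3.3 reports that the core study had already failed to show SoR non-inferior to FI. This stands as a reason not to test. It does not remove the mismatch, since an estimated difference with an interval is not a test, and the objective asks about Weeks 104 and 156, which the core study did not cover.

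A second reply is that counts will be published, so anyone can add the switch subgroups and take the difference. That is true, and a reader might wrongly infer that the comparison is lost. It is recoverable, but the plan does not produce it. Nor are intervals missing altogether: each rate has one.

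Other stronger readings are tempting and not supported:
- **That this is the only randomised comparison in the extension.** SAP 1.2 shows that dose was also randomised 1:1 in the core study. SoR versus FI is the comparison that an objective names.
- **That the analysis must be stratified.** The full analysis set definition says "If the actual stratum is different to the assigned stratum in IRT, the actual stratum will be used in analyses", and no planned summary of this endpoint is stratified. But the statement "Randomization was stratified by geographical region and by body weight collected at Visit 2" describes the initial randomisation to dose, with psoriatic arthritis history added at selected sites. The documents do not say that the Week 12 re-randomisation used these strata.
- **That the contrast would be a clean randomised effect.** Protocol 4.1 requires completion of the core treatment period and expected benefit as judged by subject and investigator. Entry was selective.

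Finally, SAP 1.12 reports that interim analyses, including a three-year one, have been done. A contrast added now would follow those looks and should say so.

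**Conclusion.** The point holds as a gap between objective and analysis. The plan names a within-dose comparison of regimens and produces no between-regimen difference or interval for the re-randomised arms. With FI at about 80%, reading overlap of the SAP's arm intervals would miss a difference interval excluding zero for observed differences of about 10 to 15 points at 148 per arm, and about 12 to 17 points at 110.

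These ranges rest on an assumed FI rate, equal arm sizes, a 95% level and complete observation of every subject; the documents fix no maintenance rates. They show the size of the problem and predict no result. The consequence is limited to a secondary, descriptive endpoint. Nothing here touches the primary safety conclusion, and nothing suggests that a hypothesis test should have been planned.

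**What to change.** In SAP 1.8.7 add one table: for 150 mg and 300 mg separately, at Weeks 104 and 156, the SoR minus FI difference in maintenance of response with a 95% Newcombe score interval. With this sign the worked example reads −11.5 points (−21.2 to −1.5).

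- Define the groups by the Week 12 re-randomised arm, pooling switchers and non-switchers, and add those groupings to Table 1-2 for this endpoint.
- State how a switcher counts in the pooled arm, because Protocol 9.4.3 treats switchers as non-responders here and SAP 1.1.1 drops the protocol's non-responder imputation without mentioning them.
- Label the table descriptive, giving selective entry and the absence of testing as reasons, and note that it was added after the interim analyses.
- Adjustment for weight and region is optional. So is a supplementary difference in PASI 75 at the same visit in both regimens, useful because the endpoint can read SoR subjects 12 weeks earlier than FI (Week 92 for 104, Week 144 for 156).

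The cost is one extra table and the pooled groupings, plus pooling of the between-arm difference across imputations if it is also reported under multiple imputation. No new data are needed, and the no-testing statement can stay.

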### **PASI 50, PASI 75, PASI 90, PASI 100 and IGA 0 or 1 response over time**

Summary statistics for PASI 50, PASI 75, PASI 90, PASI 100, and IGA mod 2011 0 or 1 response by analysis visit will be presented in contingency tables and will include absolute and relative frequencies. Confidence intervals for response rates will be derived as well based on the score method including continuity correction ([Newcombe 1998](#)).

### **PASI score over time**

Summary statistics will be provided for absolute PASI scores as well as for absolute change and percent change from baseline by analysis visit and treatment group.

### **IGA mod 2011 score over time**

Summary statistics for the IGA mod 2011 score over time will be presented by analysis visit and treatment group in contingency tables.

### **Relapse**

The number and percentage of subjects experiencing relapse will be presented by treatment group and visit.

### **Rebound or rebound like events**

The number and percentage of subjects experiencing rebound or rebound like events will be presented by treatment group as follows:

[figure not shown]
- For rebound, all assessments done up to 8 weeks after last injection will be summarized.
- Similarly for rebound like events, all assessments done up to 12 weeks after last injection will be summarized.

Subjects who received commercially available Cosentyx® will be excluded from this analysis.

